## 5.2.1 Procedures for randomisation

A dynamic randomisation approach will be applied. Randomisation codes will be generated by the Interactive Voice Response System (IVRS) / Interactive Web Response System (IWRS) provider using minimisation with biased coin assignment method which assigns patients to treatments in a clinical trial with stratifying factors on which it is desired to achieve balance.

Patients will be assigned to treatment groups using IVRS/IWRS. Routines for this will be described in the IVRS/IWRS user manual that will be provided to each centre. Randomisation codes will be assigned to patients who are eligible for randomisation.

Randomisation will be stratified for 1) use of inhaled corticosteroids and 2) pseudomonas aeruginosa infection (past or current). Patients will be randomly allocated to AZD5069 80 mg bd or placebo in a 1:1 ratio. Patients who are withdrawn after randomisation will not be replaced.

The randomisation code will be loaded into AstraZeneca Global Randomisation System (GRand).

PLEASE CHECK ITS VALIDITY BEFORE USE

AN ELECTRONIC DOCUMENT.

A PRINTED COPY OF

5 H

THIS

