#### **Statistical methods**

The primary outcome variable absolute neutrophils in sputum will be compared between AZD5069 and placebo using an analysis of variance model with fixed factors treatment and country (or centre) and using baseline as a covariate. A 2-sided 90% confidence interval (CI) will be constructed for the treatment difference and p values given. If the assumptions of ANOVA are violated, data transformation (eg, log-transformed) may be utilized or an appropriate non-parametric technique (eg, Wilcoxon rank sum) will be used instead.

The secondary outcome variables from the Bronkotest© diary card (continuous variables only), St George's Respiratory Questionnaire, lung function, 24-hour sputum weight, sputum

and blood collections will be compared between AZD5069 and placebo using an analysis of variance (ANOVA) model with fixed factors treatment and country (or centre) and using baseline as a covariate. Two-sided 90% CIs will be constructed for the treatment difference and p values given. If the assumptions of ANOVA are violated, data transformation (eg, log-transformed) may be utilized or an appropriate non-parametric technique (eg, Wilcoxon rank sum) will be used instead. In addition, a statistical analysis and summary will be produced for data derived from BDI/TDI.

All other data will be summarised and listed.

There will not be an interim analysis for this study.

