#### 12.2.1 Primary outcome variable

The primary outcome variable is:

• Change from baseline (geometric mean of the values at Visit 1a, 1b and 2) to treatment (geometric mean of the values at Visit 3a, 3b and 4) in sputum absolute neutrophils.

The primary outcome variable will be compared between AZD5069 and placebo using an analysis of variance (ANOVA) model with fixed factors treatment and country (or centre) and using baseline as a covariate. Two-sided 90% confidence intervals (CIs) will be constructed for the treatment difference and p values given. If the assumptions of ANOVA are violated, data transformation (eg, log-transformed) may be utilized or an appropriate non-parametric technique (eg, Wilcoxon rank sum) will be used instead.

The primary outcome variable analysis will be carried out on the PD analysis set.

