## 12.2.2 Secondary outcome variables

The secondary outcome variables are:

• Change from baseline (geometric mean of the values at Visits 1a, 1b and 2) to treatment (geometric mean of the values at Visit 3a, 3b and 4) in percentage neutrophils.

Approved

Date

ELECTRONIC DOCUMENT.

AN

ĿЮ

PRINTED COPY

К

5 H

THIS

PLEASE CHECK ITS VALIDITY BEFORE USE

- Change from baseline (Visit 1a or Visit 1b) to end of treatment (Visit 4) in 24-hour sputum collection weight.
- Change from baseline (Visit 2) to treatment (Visit 4) in FEV1.
- Change from baseline (Visit 2) to treatment (Visit 4) in SVC.
- Change from baseline (Visit 2) to treatment (Visit 4) in FEF25-75.
- Change from baseline (Visit 2) to treatment (Visit 4) in FVC.
- Change from baseline period (mean of last 7 days prior to start of treatment) to treatment period (mean of the last 7 days on treatment) in symptom score diary card (Bronkotest©).
- Change from baseline (Visit 2) to treatment (Visit 4) in mean total score and domain scores from St George's Respiratory Questionnaire.
- Change from baseline to treatment in sputum inflammatory markers including, but not limited to (and subject to the availability of validated assays): TNF-α, IL-8, IL-6, IL-1β, RANTES, MCP-1, GRO-α.
- Change from baseline to treatment in blood inflammatory markers including, but not limited to (and subject to the availability of validated assays): neutrophil concentration, TNF-α, IL-8, high sensitivity CRP, Amyloid-A, IL-6, IL-1β, GRO-α.
- Pharmacokinetic parameters (AZD5069 concentration measured in plasma).

The secondary outcome variables from the Bronkotest© diary card (continuous variables only), St George's Respiratory Questionnaire, lung function, 24-hour sputum weight, sputum and blood collections will be compared between AZD5069 and placebo using an analysis of variance model with fixed factors treatment and country (or centre) and using baseline as a covariate. Two-sided 90% CIs will be constructed for the treatment difference and p values given. For variables with a skewed distribution, data may be log-transformed prior to analysis or a non-parametric test (Wilcoxon rank sum) used instead. In addition, the statistical analysis and summary will be produced for data derived from BDI/TDI. The further details will be provided in the SAP.

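### Allocation is minimised on inhaled corticosteroid use and P. aeruginosa infection, yet neither factor is in the stated models, which forgoes precision to the extent that they predict the outcome after baseline adjustment

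*Protocol*

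**What the plan says.** Section 5.2.1 describes a dynamic allocation scheme, biased-coin minimisation, whose purpose is to balance the arms on chosen factors. It names two factors: "Randomisation will be stratified for 1) use of inhaled corticosteroids and 2) pseudomonas aeruginosa infection (past or current". It adds: "Patients will be randomly allocated to AZD5069 80 mg bd or placebo in a 1:1 ratio". It does not state the biased-coin probability or why these factors were chosen, and it does not list country or centre as a balancing factor.

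The analysis model is written out in three places. Section 12.2.1 specifies for the primary variable "an analysis of variance (ANOVA) model with fixed factors treatment and country (or centre) and using baseline as a covariate". Section 12.2.2 specifies for the continuous secondary variables "analysis of variance model with fixed factors treatment and country (or centre) and using baseline as a covariate". The Statistical methods part of the synopsis repeats it: "using an analysis of variance model with fixed factors treatment and country (or centre) and using baseline as a covariate". Inhaled corticosteroid (ICS) use and P. aeruginosa status appear in none of them. If the ANOVA assumptions fail, the protocol allows a transformation or a Wilcoxon rank sum test, and that test does not use the factors either.

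**The concern.** Minimisation forces the two arms to be alike on the balancing factors, so those factors contribute little to the chance variation of the treatment difference. If the model omits them, the variance between their levels stays in the residual. The reported standard error then describes a design without that balancing and exceeds the real sampling error.

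The consequences are an interval that is wider than it need be, coverage above the nominal 90%, a test that rejects less often than 5% under the null, and less power than the same data would give with the factors fitted. In a proof-of-principle study planned around 50 completers, that precision is worth having if it costs almost nothing. All of this is conditional: factors that explain nothing after baseline adjustment cost nothing when omitted.

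**Working it through.** **Inputs from the protocol.** Minimisation on two factors, 1:1 (Section 5.2.1). Model with treatment, country (or centre) and baseline (synopsis, 12.2.1, 12.2.2). SD about 1, a 50% decrease, one-sided 5%, 80% power, 25 per group, 30 per group randomised (Section 12.3).

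**Assumed, because the protocol does not give them.** Natural-log scale for the SD. R², the share of residual variance explained by the two factors after baseline and country, from 0 to 0.30. For the simulation, a coin probability of 0.8, factor prevalences of 0.5 and 0.3, and equal contributions from the two factors.

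**Step 1: reproduce the sample size.** With effect ln 2 = 0.693 and SD 1, n per group = 2 × ((1.645 + 0.842)/0.693)² = 25.7, which rounds up to 26. Power at 25 per group is 79.0% (78.0% from the t distribution). This agrees with the stated 25 to within rounding. Other scales do not: a raw difference of 0.5 gives 50, log2 gives 13 and log10 gives 137.

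**Step 2: effect of omission at 25 per group, normal approximation, exact balance.** Let s = √(1 − R²) and SE₁ = √(2/25) = 0.283, so 0.693/SE₁ = 2.451.

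- Factors fitted: the SE is s × SE₁, and power = Φ(2.451/s − 1.645).
- Factors omitted: the reported SE stays at SE₁ while the true SE is s × SE₁. Power = Φ((2.451 − 1.645)/s) and actual alpha = 1 − Φ(1.645/s).
- The interval is too wide by the factor 1/s.

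For R² = 0.10, s = 0.949 and 1/s = 1.054. Fitted power is Φ(2.583 − 1.645) = Φ(0.938) = 82.6%. Omitted power is Φ(0.806/0.949) = Φ(0.849) = 80.2%. Actual alpha is 1 − Φ(1.734) = 4.1%.

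| R² | Interval too wide by | Power omitted | Power fitted | Actual alpha, omitted |
|---|---|---|---|---|
| 0 | 0% | 79.0% | 79.0% | 5.0% |
| 0.05 | 2.6% | 79.6% | 80.8% | 4.6% |
| 0.10 | 5.4% | 80.2% | 82.6% | 4.1% |
| 0.20 | 11.8% | 81.6% | 86.3% | 3.3% |
| 0.30 | 19.5% | 83.2% | 90.0% | 2.5% |

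**Step 3: simulation of the design.** 50 patients, minimisation on two binary factors, baseline and three countries in both models, 5,000 runs per cell. The Monte Carlo error is about 0.6 points for power and 0.3 for alpha. Entries are omitted / fitted.

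| R² | Power | 90% CI width | Coverage | One-sided alpha |
|---|---|---|---|---|
| 0 | 76.1 / 75.7% | 0.975 / 0.979 | 90.4 / 90.3% | 5.1 / 4.9% |
| 0.05 | 76.4 / 77.3% | 0.979 / 0.959 | 90.6 / 89.8% | 5.0 / 5.1% |
| 0.10 | 75.9 / 78.4% | 0.975 / 0.929 | 91.5 / 89.9% | 4.4 / 5.0% |
| 0.20 | 78.4 / 83.9% | 0.978 / 0.877 | 92.5 / 90.3% | 3.3 / 4.5% |
| 0.30 | 77.8 / 86.7% | 0.981 / 0.822 | 94.6 / 90.5% | 3.0 / 4.8% |

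A second simulation of the same set-up gave power of 75/75, 77/78, 77/79, 78/83 and 78/87%. The power forgone is therefore about 0, 1, 2 to 2.5, 5 and 9 points.

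**Step 4: how much is left after baseline.** Suppose a factor effect accounts for a raw share q of the variance and is the same before and during treatment, and the correlation between baseline and on-treatment values is ρ. The residual share is then 1 − [(1 − q) − (ρ − q)²/(1 − q)]/(1 − ρ²). With q = 0.10 and ρ = 0.5 this is 1 − (0.900 − 0.178)/0.75 = 3.7%; with ρ = 0.7 it is 1 − (0.900 − 0.400)/0.51 = 2.0%. For ρ between 0.5 and 0.7 (assumed), raw shares of 10, 20 and 30% shrink to 2–4, 4–8 and 8–14%. Put into Step 2, these cost about 0.5–1, 1–2 and 2–3.5 power points.

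**The case against.** The strongest reply is that the loss may be very small. The model already adjusts for baseline, which for the primary variable is the geometric mean of three pre-treatment samples. ICS use and past or current Pseudomonas infection are fixed before randomisation, so much of any stable influence on sputum neutrophils is already in that baseline. Step 4 bears this out, and the objection stands: residual shares of 20 or 30% have no support in the protocol.

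A reader might infer that power falls below the planned 80%. The protocol does not support that. Section 12.3 assumes an SD of about 1 with no allowance for these factors, and that SD may already contain their variance. What is lost is a possible gain.

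A reader might also infer that the factors were chosen because they predict the outcome. Section 5.2.1 says only that balance is wanted. Section 1.1 does report a correlation between neutrophil numbers and pathogenic organisms, which makes some prognostic value for Pseudomonas plausible, but it gives no strength and adds that neutrophils are abundant even in patients with sterile bronchi.

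Finally, the analysis plan might add the factors. Section 12.2 does defer detail to it, but the protocol spells out the model's terms three times without them, so this is a weak defence.

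**Conclusion.** The mismatch between allocation and analysis is plain in the text, and its direction is certain: omission can only make the analysis conservative and less efficient. It does not bias the treatment estimate or inflate type I error, so a positive result would remain valid.

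The size is conditional on an unknown residual share. At 5 to 10% the loss is about 1 to 2.5 power points and the interval is about 3 to 5% too wide. At 20 to 30% it is about 5 to 9 points, but that range should be read as an upper illustration. At zero, fitting the factors makes no material difference (76.1% omitted against 75.7% fitted, within simulation error). The power figures also rest on the natural-log reading of the SD.

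This is therefore a free improvement and not a threat to the trial's validity. It concerns only the ANOVA-based endpoints. The protocol states no model for BDI/TDI or the pharmacokinetic parameters.

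**What to change.** In the synopsis and in Sections 12.2.1 and 12.2.2, add ICS use (yes/no) and P. aeruginosa infection, past or current (yes/no), as fixed factors in addition to treatment, country and baseline, using the values recorded in the IVRS/IWRS at randomisation. Say explicitly that country stays in the model.

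The cost is one sentence in each place and two degrees of freedom. With 50 patients and three countries, the residual degrees of freedom go from 45 to 43. For comparison, the permitted alternative of fitting about 14 centres would use up to 14 − 1 = 13. No new data are needed. The Wilcoxon fallback would still ignore both factors, so the gain applies only where the linear model is used, on the raw or a transformed scale.

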# 5.3 Procedures for handling subjects incorrectly enrolled, randomised or initiated on investigational product

Patients who fail to meet the inclusion/exclusion criteria should not, under any circumstances, be enrolled or randomised. There can be no exceptions to this rule.

Where patients that do not meet the selection criteria are enrolled in error but are not yet randomised the procedures included in the protocol for the discontinuation from the study must be followed.

Where patients that do not meet the selection criteria are incorrectly randomised, incorrectly started on treatment, or where patients subsequently fail to meet the study criteria postinitiation, a discussion should occur between the AstraZeneca Study Delivery Team Physician or Astra Zeneca' delegate and the Investigator regarding whether to continue or discontinue the patient from treatment. The Study Medical Monitor is to ensure all such decisions are appropriately documented. In situations where an agreement cannot be reached, the patients should have their study therapy stopped and be discontinued from the study.

## 5.4 Blinding and procedures for unblinding the study

## 5.4.1 Methods for ensuring blinding

AZD5069 will be provided as a capsule for oral administration and with a matching placebo. Capsules of AZD5069 will be provided in the strength of 20 mg.

As the leucocyte count (including neutrophil data) will potentially be unblinding to site and study personnel, the data will be transferred from the local laboratory performing the analysis to the central laboratory. The results for Visits 1 and 5 will be communicated to the sites, but for all other visits (Visits 2 to 4) the central laboratory will review the data and notify the site if a patient needs to be recalled for repeat sampling or needs to be withdrawn from the study. Furthermore, to ensure that the investigator is not unblinded by only patients on active treatment being recalled, a number of patients with a normal leucocyte count will be randomly selected for repeat leucocyte assessments. Full details of the above process are detailed in the laboratory specifications.

## 5.4.2 Methods for unblinding the study

Individual treatment codes, indicating the treatment randomisation for each randomised patient, will be available to the investigator(s) or pharmacists from the IVRS/IWRS. Routines for this will be described in the IVRS/IWRS user manual that will be provided to each centre.

A copy of the randomisation scheme will also be made available to the PK bioanalyst, to enable the analysis of samples from patients who have received active treatment to be prioritised. This documentation will be placed in a secure location until the end of the study.

The treatment code should not be broken except in medical emergencies when the appropriate management of the patient requires knowledge of the treatment randomisation. The investigator documents and reports the action to AstraZeneca or AstraZeneca's representative,

## 35(76)

and study medical monitor without revealing the treatment given to the patient to the AstraZeneca staff.

AstraZeneca retains the right to break the code for SAEs that are unexpected and are suspected to be causally related to an investigational product and that potentially require expedited reporting to regulatory authorities. Treatment codes will not be broken for the planned analyses of data until all decisions on the evaluability of the data from each individual patient have been made and documented.

## 5.5 Treatments

### 5.5.1 Identity of investigational product(s)

The investigational product (IP) will consist of 20 mg capsules of AZD5069.

AstraZeneca will supply the IP to the investigators via an IVRS/IWRS. The IP will be supplied as capsules for oral use according to the description in Table 5.

Placebo will be supplied as capsules matching AZD5069 to ensure the blinding of the study treatment.

Fable 5	Identity of investigational products
----------------	--------------------------------------

Investigational product	Dosage form and strength	Manufacturer
AZD5069	Capsule 20 mg	AstraZeneca R&D,
Placebo for AZD5069	Capsule	AstraZeneca R&D,

Note: The batch number will be detailed in the Clinical Study Report (CSR).

## 5.5.2 Doses and treatment regimens

Patients will be advised to have food (meal) just before attending Visit 2 (Day 1) where they will be randomised in a 1:1 ratio to receive either AZD5069 capsules 80 mg or placebo capsules orally bd for 28 days ( $\pm$ 2 days). The first dose should be administered within 30 minutes of having food (meal) and with 100 mL water, in the clinic in the morning of Day 1.

At Visit 2, patients will receive 1 study drug kit (one box) including 4 blister cards. Each blister card will have 16 blister pockets with 4 capsules of 20 mg AZD5069 or corresponding placebo in each pocket. One kit (1 box) will be issued to the randomised patients, sufficient to allow self-dosing until Visit 4.

At Visit 3 (Day  $14 \pm 2$  days) patients will be advised to have food (meal) just before attending the clinic in the morning, having withheld taking their dose of study medication, which will be taken in the clinic and administered with 100 mL of water. One kit will be issued to the randomised patients, sufficient to allow self-dosing until Visit 4.

#### 36(76)

Approved

AN

PRINTED COPY OF

R

5 H

THIS

ELECTRONIC DOCUMENT. PLEASE CHECK ITS VALIDITY BEFORE USE
At Visit 4 (Day  $28 \pm 2$  days) patients will be advised to have food (meal) just before attending the clinic in the morning, having withheld taking their dose of study medication. Patients should take their last dose(s) of study medication in the clinic with 100mL water. There should only be 1 dose administered on this final day.

All other doses (ie, those not administered in the clinic) should be taken with approximately 100 mL water, within 30 minutes of food (meal) intake.

## 5.5.3 Additional study drug

No additional study drug will be provided for this study.

## 5.5.4 Labelling

Labels will be prepared in accordance with Good Manufacturing Practice (GMP) and local regulatory guidelines. The labels will fulfil GMP Annex 13 requirements for labelling. Label text will be translated into local language.

The packaging and labelling will be performed by Investigational Products (IPS) AstraZeneca R&D Mölndal, Sweden. All supplies and labels will be prepared in accordance with GMP and local regulatory guidelines.

Each study drug kit (box), which contains 4 blister cards, will be labelled with a single-panel label without a tear-off part. Each blister card will be labelled with a small single-panel label.

## 5.5.5 Storage

All study drugs should be kept in a secure place under appropriate conditions. The IP labels specify the appropriate storage.

## 5.6 **Concomitant and post-study treatment(s)**

## 5.6.1 Medication allowed during the study

Patients are allowed to continue long-acting muscarinic antagonists (LAMA), long-acting beta agonists (LABA), LABA/ inhaled corticosteroids (ICS) combinations unchanged throughout the study if they are already on these, but if possible should withhold these before lung function testing (see Section 5.6.2).

## 5.6.2 Restricted medication

As far as possible patients should withhold LAMA/LABA for 12 hours, short-acting beta agonists (SABA) for 6 hours and short acting muscarinic antagonists (SAMA) for 8 hours before their lung function tests. After they have had the test they may take their normal dose of the medication.

AN ELECTRONIC DOCUMENT. PLEASE CHECK ITS VALIDITY BEFORE USE

A PRINTED COPY OF

5 H

THIS

#### 5.6.3 Disallowed medication

In addition, the following treatments are not allowed:

- Use of oral corticosteroids in the 30 days prior to Visit 2 and throughout the study (NB: use of inhaled corticosteroids is allowed)
- Use of non-prophylactic antibiotics, systemic or nebuliser, in the 4 weeks prior to Visit 2 and throughout the study (NB: prophylactic use is allowed)
- Treatment with immunomodulatory agents within 8 weeks prior to Visit 2 and throughout the study
- Herbal medications, including but not limited to St John's Wort and Echinacea within 3 weeks prior to Visit 2 and throughout the study.

Although it is not expected from both non-clinical and in vitro data that AZD5069 at the dose to be used in this study will have any significant drug interactions, the following medications will not be allowed throughout the dosing period (ie, Visits 2 to 4):

- CYP2B6 substrates, in the 4 weeks prior to Visit 2, such as but not limited to: bupropion, cyclophosphamide, efavirenz, ifosfamide, selegiline, alfentanil, nevirapine, propofol, tamoxifen, valproic acid, artemisinin, pethidine, modafinil, sertraline, thiotepa
- PgP substrates, in the 4 weeks prior to Visit 2, including but not limited to: quinidine, tacrolimus, ivermectin, colchicines, etoposide, doxorubicin, vinblastine, protease inhibitors, non-nucleoside reverse transcriptase inhibitors, cyclosporin, digoxin
- Warfarin in the 4 weeks prior to Visit 2 and until completion of the study follow-up visit (Visit 5).

Any other drugs including inhaled and oral respiratory drugs could be allowed provided their doses have been stable for at least 4 weeks before enrolment and the doses remain unchanged throughout the study. SABA and/or SAMA may be taken as needed for symptomatic control of breathlessness.

Other medication which is considered necessary for the patient's safety and well-being, may be given at the discretion of the investigator and should be recorded in the electronic case report form (eCRF).

Please refer to Section 5.1 for other restrictions during the study.

